3.5. Methods of Pooling Data

Pooling of data is not applicable to this study.

3.6. Adjustments for Covariates

No statistical analyses or statistical models that adjust for possible covariate effects are planned.

3.7. Multiple Comparisons/Multiplicity

There are no tests of hypotheses. Data will be analyzed descriptively.

3.8. Subpopulations

No analyses of subject subgroups are planned.

3.9. Withdrawals, Dropouts, Loss to Follow-up

Subjects who are withdrawn or discontinue from the study will not be replaced.

3.10. Missing, Unused, and Spurious Data

In general, there will be no substitutions made to accommodate missing data points. All data recorded on the case report form will be included in data listings that will accompany the clinical study report.

When tabulating adverse event data, partial dates will be handled as follows. If the day of the month is missing, the onset day will be set to the first day of the month unless it is the same month and year as study treatment. In this case, to conservatively report the event as treatment-emergent, the onset date will be assumed to be the date of treatment. If the onset day and month are both missing, the day and month will be assumed to be January 1, unless the event occurred in the same year as the study treatment. In this case, the event onset will be coded to the day of treatment in order to conservatively report the event as treatment-emergent. A missing onset date will be coded as the day of treatment.

3.11. Visit Windows

It is expected that all visits should occur according to the protocol schedule. All data will be tabulated per the evaluation visit as recorded on the CRF even if the assessment is outside of the visit window. In data listings, the relative day of all dates will be presented.

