Clinical Study Sites:	Participants will be recruited from up to 10 clinical study sites. Clinical sites must have participated in the multicenter Phase 1/2 extension study, NTMT-01/02E, or the Phase 3 (NTMT-03) study of NT-501 in participants with Macular Telangiectas Type 2 (MacTel).			
Number of Participants:	The goal is to have a minimum of 30 evaluable participants			
Structure:	Multicenter, Open-Label			
Visit Schedule:	There will be a maximum of 7 visits over a study period of up to 7 months. These visits will include Visit 1, Screening (Day -28 to Day -1); Visit 2, Surgery; Visit 3, Post-Surgery Day 1; Visit 4, Post-Surgery Week 1; Visit 5, Post-Surgery Month 1; Visit 6, Post-Surgery Month 3; Visit 7, Post-Surgery Month 6 and Exit Visit.			
Duration:	The study duration will be approximately 7 Months (screening period of up to 28 days plus a follow-up period of 6 months).			

Study Description:	This is a multicenter, open-label, study to evaluate the safety of bilateral NT-501 implants in a minimum of 30 study participants with MacTel type 2. All study subjects who have received a NT-501 implant in one eye through participation in the Phase 1/2 extension study, NTMT-01/02E, or the Phase 3 (NTMT-03) study and meet the eligibility criteria, will receive a NT-501 implant in their fellow eye and will be followed for 6 months following the NT-501 implantation.			
Inclusion Criteria:	Study eligibility is to be assessed at Visit 1 (Screening). To participate in this study, the potential participant must meet all the following criteria:			

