6.2 Description of the Study Procedures

6.2.1 Study Procedures

The following examinations are to be performed at the times indicated in the schedule of study procedures, where 1 month is defined as 30 days. Additional information related to these examinations is provided in the procedure specific instructions. All ocular evaluations/procedures will be completed only in the study eye unless otherwise indicated.

- Medical evaluation, as would be standard for any surgical procedure and its associated anesthesia (the tests to be performed will be site-specific); evaluation may be performed during the screening period or on the day of surgery
- Complete ophthalmic examination including:
 - External examination of the eye and adnexa
 - Pupil responsiveness
 - Manifest refraction
 - Slit lamp biomicroscopy
 - Dilated fundus examination
 - Indirect ophthalmoscopy
 - Goldmann applanation tonometry
 - BCVA (this assessment will be performed using the ETDRS visual acuity procedure, administered by a certified technician)
 - Measurement of undilated pupil diameter
- Ophthalmic assessments including:
 - SD-OCT
 - Fluorescein angiography
 - Color fundus photography
 - o External photograph of conjunctiva over implant
- Urine or blood pregnancy test for premenopausal female participants
- Serum chemistry, hematology, and urinalysis
- Serum analyses of CNTF, Ab and Nab to CNTF, Ab to NTC-201.6A cells and Ab to DFHR

Goldmann applanation tonometry, measurement of undilated pupil diameter, slit lamp biomicroscopy, dilated fundus examination, and urine or blood pregnancy testing will be performed following standard procedures at each site.

In the event of extenuating circumstances whereby an in-clinic follow-up visit cannot be conducted within the designated visit window, a Safety Check-In call should be performed, and an out of window in-clinic visit should be performed as soon as possible. Following a missed or out of window visit, every effort should be made to return the participant to the original protocol-specified visit schedule.

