6.3.7 Visit 7: Six-Month Post-surgery (+/-14 days)

Participants must return to the clinic 6-months post-surgery and will undergo the following procedures:

- AE assessment
- Review concomitant medications and concurrent non-study procedures
- BCVA following manifest refraction (both eyes)
- Blood sample collection for analysis of Ab and Nab to CNTF, Ab to NTC-201.6A cells and Ab to DFHR
- Blood sample collection for analysis of serum levels of CNTF
- Complete ophthalmic exam (consisting of an external examination of the eye and adnexa, screening for pupil responsiveness, slit lamp biomicroscopy, dilated fundus examination, indirect ophthalmoscopy, and IOP) (both eyes)
- Measurement of undilated pupil diameter (both eyes)
- SD-OCT (both eyes)
- Implant site examination (both eyes)
- External photograph of conjunctiva over implant (both eyes)
- Color digital fundus photography (both eyes)

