18 STUDY DISCONTINUATION

Both the sponsor and the principal investigator reserve the right to terminate the study at the investigator's site at any time. Should this be necessary, the sponsor or a specified designee will inform the appropriate regulatory authorities of the termination of the study and the reasons for its termination, and the principal investigator will inform the IRB/IEC of the same. If the decision is made to terminate the study, the sponsor and the principal investigator will assure that adequate consideration is given to the protection of the participants' interests.

The investigator may discontinue a participant from the study if warranted. The investigator and the sponsor may also request the withdrawal of a participant because of noncompliance (e.g., missed visits), administrative reasons, or any other valid and ethical reasons.

Reasons for participant discontinuation may include, but are not limited to, the following:

- Investigator determination that it is not in the best interest of the participant to continue participation
- Intercurrent illness
- AE that is serious and unexpected
- Worsening condition
- Any other safety concerns
- If a participant withdraws or is discontinued from the study, they should return for an exit visit. The schedule of assessments for this visit is the same as that for the 6-month visit.

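### If early exits are recorded as Visit 7, as the visit schedule implies, SAP 3.11 puts their results in the Month 6 column however early they were collected; one SAP sentence would prevent this

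*SAP*

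**What the plan says.** **Exit visit.** Protocol section 18: "If a participant withdraws or is discontinued from the study, they should return for an exit visit". On its content: "The schedule of assessments for this visit is the same as that for the 6-month visit".

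**Visit schedule.** The protocol synopsis says "There will be a maximum of 7 visits over a study period of up to 7 months" and names the last one "Visit 7, Post-Surgery Month 6 and Exit Visit". Protocol Table 1 and SAP Table 1-1 place the Exit Form at Visit 7 only. Neither table lists an early-termination visit.

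**Tabulation.** SAP 3.11: "All data will be tabulated per the evaluation visit as recorded on the CRF even if the assessment is outside of the visit window". Actual timing is shown elsewhere: "In data listings, the relative day of all dates will be presented".

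**Handling of withdrawals.** SAP 3.9 says only that participants who leave are not replaced. SAP 3.10 covers missing data and partial adverse event dates. Protocol 11.3.1 evaluates participants who discontinue on the visits they attended, but does not assign the exit visit to a time point.

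**Results reported at Month 6.** These are serum CNTF (SAP 4.4.1), BCVA loss of at least 15 letters (SAP 4.4.2) and four antibody measures with titers and fold-rise (SAP 4.4.3). Protocol 11.3.1 also plans to report antibodies to CNTF, neutralizing antibodies and antibodies to NTC-201.6A that are seen at Month 3 and still present at Month 6.

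**The concern.** In a descriptive safety study the time-point label is part of the result. A reader takes a Month 6 column to describe participants about 180 days after the second implant. Under the rules above, it may also contain participants who left much earlier.

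Those participants are unlikely to be typical. The reasons for discontinuation listed in Protocol section 18 include serious unexpected adverse events, worsening condition and other safety concerns. The error can go either way: an early post-operative acuity loss would raise the Month 6 proportion, while an early antibody-negative sample would lower it. The antibody persistence summary is the most exposed, because it depends entirely on which sample carries the Month 6 label.

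**Working it through.** The plan gives no figure to reproduce. The sample size rests on feasibility and there is no hypothesis test. The check is a reading of the rules together, then an illustration of size.

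**1. The chain of rules**

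- An early exit receives the Month 6 assessments: explicit, Protocol section 18.
- Tables follow the CRF visit whatever the date: explicit, SAP 3.11.
- An early exit is recorded as Visit 7: inferred. Visit 7 is the only scheduled exit visit and the only place for the Exit Form, but the CRF is not available.
- A rule keeps early-exit records out of Month 6: none found in SAP 3.9 to 3.11, SAP 4.4 or Protocol 11.3.1.

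**2. How early the data could be**

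The Month 6 window is 180 ± 14 days, so Day 166 to Day 194. For an exit on Day d, the gap before the window opens is 166 − d:

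- Day 14: 152 days
- Day 30: 136 days
- Day 60: 106 days
- Day 90: 76 days

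**3. Effect of one record**

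Take N = 30 (the protocol minimum), one early exit and x events among the other 29. This assumes that the denominator is participants with a record at that visit.

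- Exit record has the event: (x + 1)/30 − x/29 = (29 − x)/870. The largest value is at x = 0: 29/870 = 3.3 points.
- Exit record has no event: x/30 − x/29 = −x/870. At x = 3 this is −0.3 points.

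**4. Several early exits**

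The documents give no discontinuation rate, so the number of early exits k is an assumption, shown over a range. Intervals are Clopper-Pearson 95%, the SAP's own method for proportions.

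| k | In-window events | In-window only | Exits pooled, none with event | Exits pooled, all with event |
|---|---|---|---|---|
| 1 | 0 | 0/29 = 0% (0 to 11.9) | 0/30 = 0% (0 to 11.6) | 1/30 = 3.3% (0.1 to 17.2) |
| 1 | 3 | 3/29 = 10.3% (2.2 to 27.4) | 3/30 = 10.0% (2.1 to 26.5) | 4/30 = 13.3% (3.8 to 30.7) |
| 3 | 0 | 0/27 = 0% (0 to 12.8) | 0/30 = 0% (0 to 11.6) | 3/30 = 10.0% (2.1 to 26.5) |
| 3 | 3 | 3/27 = 11.1% (2.4 to 29.2) | 3/30 = 10.0% (2.1 to 26.5) | 6/30 = 20.0% (7.7 to 38.6) |
| 5 | 3 | 3/25 = 12.0% (2.5 to 31.2) | 3/30 = 10.0% (2.1 to 26.5) | 8/30 = 26.7% (12.3 to 45.9) |

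With three in-window events, pooling shifts the proportion by −0.3 to +3.0 points for k = 1 and by −2.0 to +14.7 points for k = 5. The upper ends require every early exit to have the event. The intervals overlap in every row.

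**5. Antibody persistence**

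Suppose a participant is antibody-positive at Month 3 on Day 90, then leaves and gives an exit sample on Day 100 that is recorded as Visit 7. If that sample is positive, the antibody counts as persisting to 6 months after 100 − 90 = 10 days, with the sample taken 166 − 100 = 66 days before the Month 6 window opens.

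**The case against.** The strongest objection is that the Visit 7 label is not stated. Section 18 fixes the content of the exit visit, not its name, and the synopsis may only be describing completers, for whom Month 6 is the exit. SAP 3.11 acts on what the CRF records, and a CRF with an early-termination or unscheduled label would keep these data out of Month 6. This stands, so the point is conditional. A reader might infer that the documents require early exits to be reported as Month 6; they do not. But even a separate label would leave the SAP silent on where those records go in the by-visit tables.

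A reader might also infer that tabulating late make-up visits under their planned visit is an error, and that all data should be reassigned by study day. The documents do not support that. Protocol 6.2.1 says that after a missed window "an out of window in-clinic visit should be performed as soon as possible", and SAP 3.11 states in advance how such visits are tabulated, which is an acceptable choice. Strict use of the protocol windows (Days 5 to 9, 23 to 37, 76 to 104 and 166 to 194) would leave Days 10 to 22, 38 to 75 and 105 to 165 unassigned and drop genuine late visits from the tables.

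The impact is also limited. The primary endpoints are adverse event summaries from surgery to 6 months and carry no visit label. BCVA loss is also summarized at any follow-up visit, and no analysis of persistent BCVA loss is planned. Withdrawals and their reasons are tabulated, and listings show the study day. Protocol 18.1 expects few discontinuations and lets a participant whose implant is removed remain on the planned visits. All of this stands and keeps the point small.

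**Conclusion.** The point holds as a conditional gap in the SAP. If early exits are recorded as Visit 7, the stated tabulation rule mislabels their BCVA, serum CNTF and antibody results as Month 6, and no other rule prevents it. Each record shifts a Month 6 proportion by up to about 3 points at N = 30, in a direction that cannot be predicted.

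This rests on three assumptions: the Visit 7 label, at least one withdrawal with an exit visit before Day 166, and denominators based on participants with a record at the visit. A reader might infer that the study's main safety conclusions are at risk. They are not: the adverse event endpoints and the any-visit BCVA summary do not change, and there is no test whose error rate could be affected. This is an inexpensive improvement to the SAP rather than a flaw in the design.

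**What to change.** Add to SAP 3.11 that an exit visit of a withdrawn or discontinued participant before Day 166:

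- is shown in a separate early-exit row of the by-visit tables and not as Month 6;
- is not used to judge antibody persistence to 6 months;
- stays in the any-follow-up-visit BCVA summary and in the listings with its study day.

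Report the number of such visits. Leave scheduled and make-up visits under their nominal visit, as now planned.

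The cost is a short addition to the SAP and one derived analysis-visit variable, with no new data and no change to study conduct. The downside is a slightly smaller Month 6 denominator. For example, with three early exits and no events, the upper confidence limit is 12.8% (0/27) rather than 11.6% (0/30).

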3.12. Interim Analyses

No interim analyses are planned for this study.

4. STUDY ANALYSES

4.1. Subject Disposition

Subject disposition will be tabulated and include the total number screened, the total number treated, the number who withdrew prior to completing the study and reason(s) for withdrawal..

A by-subject data listing of study completion information including the reason for premature study withdrawal, if applicable, will be presented.

4.2. Demographics and Baseline Characteristics

Demographics, baseline characteristics, medical history, ophthalmic history, vital signs, hematology, chemistry, and urinalysis will be displayed descriptively and through listings. Demographic characteristics (age, sex, body mass index [BMI], and race), and baseline characteristics (Number of correct letters on BVCA by both eyes, spectral domain coherence tomography by both eyes, and baseline CNTF serum level).

Number of subjects, mean, SD, median, minimum, and maximum will be presented for continuous measures; number and percentage of subjects will be presented for categorical measures. The Safety population will be used. No formal statistical comparisons will be performed.

Subjects who report multiple races will be counted for each race reported.

Medical history will include the overall incidence of any finding. Details will be provided in a listing.

4.3. Evaluation of Primary Safety Endpoints

All analyses will be conducted using the safety population.

All AEs will be coded using the MedDRA coding system and displayed in tables and data listings using system organ class (SOC) and preferred term.

Analyses of adverse events will be performed for those events that are considered treatment-emergent, where treatment-emergent is defined as any adverse event with onset after the day of surgical implantation through the end of the study (Month 6 ± 14 days post surgery), or any event that was present at baseline but worsened in intensity or was subsequently considered study-related by the Investigator through the end of the study.

Adverse events are summarized by subject incidence rates. In these tabulations, each subject will contribute only once (i.e., the most related occurrence or the most intense occurrence) to each of the incidence rates in the descriptive analysis, regardless of the number of episodes.

The number and percent of subjects will be tabulated overall, by SOC and preferred term within SOC for the following endpoints.

- Treatment-emergent adverse event (TEAE)
- Treatment-related TEAE
- Ocular TEAE occurring in the study eye
- Ocular TEAE occurring in the fellow eye
- Treatment-related Ocular TEAE
- TEAE by maximum grade
- Serious Adverse Events
- TEAEs leading to discontinuation

No formal hypothesis-testing analysis of adverse event incidence rates will be performed.

By-subject listings also will be provided for the following: subject deaths, serious adverse events, and adverse events leading to withdrawal.

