3 STUDY ENDPOINTS

Primary Safety Endpoints

- Number and proportion of adverse events from day of surgery through 6 months post implantation
- Number and proportion of severe adverse events from day of surgery through 6 months post implantation
- Number and proportion of ocular adverse events from day of surgery through 6 months post implantation
- Number and proportion of non-ocular adverse events from day of surgery through 6 months post implantation

Secondary Safety Endpoints

- Number and proportion of participants with a loss in BCVA of 15 or more letters from baseline in the study eye using the Early Treatment Diabetic Retinopathy Study (ETDRS) distance chart
- Number and proportion of participants with at least 1 treatment-emergent serious adverse event (SAE)
- Detectable serum levels of CNTF at Months 1, 3 and 6 post-implantations of NT-501
- Number and proportion of participants with serum Ab or Nab to CNTF, Ab to NTC-201.6A cells and Ab to DFHR at Baseline and Months1, 3 and 6 post-implantation of NT-501

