6.3.2 Visit 2: Enrollment and Surgery

If the participant meets all study criteria and agrees to participate in the study, then the implant surgery date should be identified. The implant surgery procedure should be completed within one month of the Screening visit.

On the date of the surgery, the investigator will confirm that no change in the participant's general condition has occurred that would exclude study participation.

The following evaluations/procedures will be conducted during this visit:

- Eligibility review
- Medical evaluation that is standard for any surgical procedure and its associated anesthesia (the specific tests to be ordered will be site-specific), unless the medical evaluation was performed during screening period
- Record any further medical/ophthalmic history
- Record any additional concomitant medications and non-study procedures
- Perform AE assessment (from the time surgery begins)
- Assess BCVA (may be performed within 1 week prior to the day of surgery or on the day of surgery, manifest refraction is not required)
- NT-501 implant surgery

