1.3.6. Primary Safety Parameters

Safety evaluations that will be performed during the study include physical examinations, measurement of vital signs, clinical laboratory evaluations including hematology, serum chemistry, and urinalysis, and monitoring of adverse events and concomitant medications. Serum chemistry, hematology, and urinalysis will be performed only at baseline.

Primary safety endpoints are:

- Number and proportion of adverse events from day of surgery through 6 months post implantation
- Number and proportion of severe adverse events from day of surgery through 6 months post implantation
- Number and proportion of ocular adverse events from day of surgery through 6 months post implantation
- Number and proportion of non-ocular adverse events from day of surgery through 6 months post implantation

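### Treatment-emergent AEs are counted from the day after surgery, so new Day 0 events and new events imputed to Day 0 drop out of the primary safety tables

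*SAP*

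**What the plan says.** The primary endpoints in Protocol 3 and SAP 1.3.6 include the day of surgery. The first reads "Number and proportion of adverse events from day of surgery through 6 months post implantation"; the severe, ocular and non-ocular endpoints use the same window, for example "Number and proportion of ocular adverse events from day of surgery through 6 months post implantation". Protocol 6.3.2 starts AE assessment when surgery begins, and Protocol 9.1 records AEs from surgery to the last visit.

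SAP 4.3 then sets the scope of the tables: "Analyses of adverse events will be performed for those events that are considered treatment-emergent". Its definition has two limbs. The first is by onset: "treatment-emergent is defined as any adverse event with onset after the day of surgical implantation through the end of the study". The second admits "any event that was present at baseline but worsened in intensity or was subsequently considered study-related by the Investigator".

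SAP 3.2 designates the day of implantation as Day 0. SAP 3.10 deals with incomplete onset dates. If the day is missing and the month and year are those of treatment, it says: "In this case, to conservatively report the event as treatment-emergent, the onset date will be assumed to be the date of treatment". It does the same, for the same stated reason, when day and month are missing and the year is that of treatment. Finally: "A missing onset date will be coded as the day of treatment". SAP 5 declares no departure from the protocol's analyses.

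**The concern.** The table definition is narrower than the endpoint it is meant to report, by exactly one day, and that day is the day of the operation. Protocol 1.1.4 says that most AEs with this implant have been related to the implantation procedure and that the majority resolved within a few days. Protocol 9.3 describes procedure-related events as those occurring straight after surgery, or later if directly related to it. Protocol 12 lists pain, bleeding and retinal detachment among the surgical risks. In a study whose only primary question is safety, the tables would leave out the day on which procedural events can first begin. Any AE category with new Day 0 events could be understated, never overstated.

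The imputation rule turns against its own purpose. It assigns uncertain onsets to the surgery date so that they are kept, and 4.3 then drops that date. Some of these events will truly have started after surgery and would have qualified had the date been complete.

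**Working it through.** The documents give no sample size, power or expected AE rate, so there is no planned figure to reproduce. The check applies the SAP's rules as written.

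**Inputs.** Surgery = Day 0 (SAP 3.2). First limb: onset day > 0. Second limb: present at baseline, and worsened or later judged related (SAP 4.3). Baseline: the last measurement before study-eye implantation (SAP 3.4), so a new event during or after surgery was not present at baseline. Imputation as in SAP 3.10. N = 30, the minimum in Protocol 5.1.

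**Step 1: classify test events**

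| Event | Onset day used | Treatment-emergent under SAP 4.3 | If the first limb is onset day ≥ 0 |
|---|---|---|---|
| New, intraoperative | 0 | No | Yes |
| New, same day after surgery | 0 | No | Yes |
| New, day missing, surgery month | 0 (imputed) | No | Yes |
| New, day and month missing, surgery year | 0 (imputed) | No | Yes |
| New, date fully missing | 0 (imputed) | No | Yes |
| New, first day after surgery | 1 | Yes | Yes |
| New, day missing, later month | first of that month | Yes | Yes |
| Baseline condition that worsened on Day 0 | 0 | Yes (second limb) | Yes |

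All five kinds of new event dated or imputed to Day 0 fail the definition as written and pass once Day 0 is included. The other three rows do not change.

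**Step 2: one event in 30.** If one participant has a new sight-threatening event on Day 0 and no other event of that kind, the table shows 0/30. The correct figure is 1/30 = 3.3%, Clopper-Pearson 95% CI 0.1% to 17.2%.

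**Step 3: possible effect on incidence (assumed rates).** Each participant counts once per tabulated rate, so a participant is lost from a row only if all of their events in that row began on Day 0. Let p be the true proportion with an ocular AE and f the share of those whose ocular onsets were all on Day 0. Reported incidence = p × (1 − f). With p = 0.60 assumed:

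- f = 0.25: 0.60 × 0.75 = 45%
- f = 0.50: 0.60 × 0.50 = 30%
- f = 0.75: 0.60 × 0.25 = 15%

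A second view takes independent probabilities p0 of at least one Day 0 AE and p1 of at least one AE from Day 1 on. Expected participants with an event are 30 × p1 under the SAP text and 30 × [1 − (1 − p0)(1 − p1)] with Day 0 included:

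- p0 = 0.2, p1 = 0.6: 18.0 against 30 × (1 − 0.8 × 0.4) = 20.4
- p0 = 0.5, p1 = 0.3: 9.0 against 30 × (1 − 0.5 × 0.7) = 19.5
- p0 = 0.8, p1 = 0.3: 9.0 against 30 × (1 − 0.2 × 0.7) = 25.8

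Depending on the assumed rates, the shortfall is small or large.

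**The case against.** The best reply is that this is a slip of drafting. SAP 1.3.6 and 3.10 both show that Day 0 was meant to count, and a programmer might include it anyway. Nor would a serious Day 0 event vanish from the report. All case report form data are listed (SAP 3.10), there are by-subject listings of deaths, SAEs and AEs leading to withdrawal, and the SAE row in 4.3 is not labelled treatment-emergent. A loss of 15 or more letters at a follow-up visit would be counted under SAP 4.4.2 whatever the AE onset date. Finally, the schedule has no complete ophthalmic exam on Day 0; signs first found at the Day 1 exam may be recorded with Day 1 onset and so be kept.

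Some of this stands. The second limb keeps pre-existing conditions that worsen on Day 0, so the loss concerns new events. It is a loss from tables, not from the database. The Day 0 share is unknown, and a procedure-related event need not begin on Day 0. The conservative intent is stated only for partial dates, although fully missing dates meet the same fate.

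None of it removes the conflict. The primary endpoints are numbers and proportions, which listings do not supply. The opening sentence of the definition restricts all AE analyses, the SAE row included, and the secondary SAE endpoint is itself limited to treatment-emergent events. Even if the second limb is read loosely, so that any event later judged related qualifies, unrelated Day 0 events and imputed events not judged related are still lost. A programmer who includes Day 0 departs from the written SAP.

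**Conclusion.** The concern holds. SAP 4.3 contradicts the primary endpoints in both documents and defeats the SAP's own imputation rule. Followed literally, it removes from the primary safety tables every new event with onset on Day 0 and every new event whose onset is imputed to Day 0. That conclusion rests on the text alone. How far reported rates would fall cannot be determined, because the documents give no Day 0 event rate; the percentages and expected counts in the working rest on assumed rates and only show the range. The direction is certain: a reported rate is either unchanged or too low. With about 30 participants, a single event decides whether a table row shows zero. Because this governs the primary safety result, it must be corrected before the analysis.

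**What to change.** In SAP 4.3, change the first limb of the definition so that an event qualifies if its onset is on or after the start of study-eye surgery on Day 0. Leave the end of the window and the second limb as they are. SAP 3.10 then works as intended without amendment, and the tables match the endpoints in Protocol 3 and SAP 1.3.6.

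The cost is one sentence. No new data are needed, and no onset times either, because Protocol 9.1 records AEs only from surgery onwards. Reported AE rates will stay the same or rise; by how much depends on how many events begin on, or are imputed to, Day 0.
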